The participants will be asked not to move the head quickly in the magnetic field to avoid potential sensation of dizziness, occurring in 30% or more of subjects. The participants may experience a metallic taste while entering or leaving the scanner. This is also a relatively

common sensation. The participants may experience a headache during or after the scan. This is infrequent and occurs in about 5% of volunteers. Another less common occurring is seeing tiny light flashes when the eyes are closed. In studies at 8 Tesla, 1 subject out of 200 has vomited as the result of being in the scanner.

Exposure to the rapidly changing magnetic fields could cause twitching of the subject's muscles. This effect, known as peripheral nerve stimulation (PNS), is temporary.

As with all MRI, any metal in the body or in clothing represents a risk. Metallic objects can be accelerated by the magnetic field and become dangerous. A metal implant or foreign object in the body could be displaced by the magnetic field. There can be increased heating near metal structures. Safety screening for unsafe metals by the PI and AIRC Director in conjunction with the 7T development plan will ensure this risk is minimized. Potential risks of EEG are possible scalp irritation resulting from the cap of sensors, boredom and fatigue. If the participant becomes excessively uncomfortable, the experimenter will stop the experiment at any time.

Participants undergoing tDCS may experience the following side effects but such are still considered to represent a minimal risk. 1) The most common side effect is temporally local redness of the skin direct under the electrode. This disappears within 1 hour. 2) They may experience itching at the site of the electrode, which also passes within an hour. 3) A small number of patients have a slight feeling of dizziness when starting the stimulation. This lasts only a few seconds and does not affect balance after stimulation. 4) Very rarely, temporary skin damage, or a burn may occur under the electrode. This gives a darkening or peeling of the top layers of skin, which normalizes after a week and heals. The size of such etch is a few millimeters. This is harmless, however, with the current that we will handle, this risk is minimal. 5) On the safety side, transcranial direct current stimulation is considered safe.

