Participants will be monitored by a clinician during administration of tDCS. Should the participant become dizzy or experience other side effects during the procedure, reassurance will be provided and they will be encouraged to continue. In the case of a itching or burning sensation, participants will be encouraged to move the arm band, and inform researchers of any irritation. If necessary, the procedure will be discontinued. If there is a burn which occurs that is evident to participant or researchers and warrants treatment, the participant will be referred to seek immediate treatment with the Urgent Care center, or follow up with their primary care physician.

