RISK/BENEFIT ASSESSMENT: The disadvantages to being in this study include: time commitment, travel, and the physical and emotional challenges related to assessments and trainings. The maximum time planned for each of the MRI/MRS scan is 1 hour and each of neuropsychological and experimental behavioral assessment session is up to 2 hours not including time for commuting and scheduling for a total of 6 hours for participating in the study. Although the 7T MRI scanner is not FDA approved for clinical use, the scanner will be operated

within the FDA guidelines for high-field imaging. The procedures and training sessions could take less time, but the investigators want to prepare the participants for the possibility of the maximum time commitments. TDCS is a non-invasive technique which has been shown to be safe in healthy subjects in several research centers in previous investigations, with no impact to participant well-being. Individuals with a history of seizures, pregnancy, cardiac history or those who have a pacemaker will be excluded as a precaution. A referral plan is in place for those who have topical skin damage from tDCS. There is a risk of breach of confidentiality, although investigators are taking careful precautions to prevent this. Participants are informed of the risks prior to signing the consents.

BIOSTATISTICS:

Our primary hypotheses for all outcome measures, including imaging and EEG, involve interactions of experimental group with pre- and post-assessment time periods. We expect that tDCS-SMART will have larger post-training improvements for behavioral outcomes, EEG components, and imaging biomarker changes relative to tDCS-SHAM. These will be assessed by simple interaction tests in general statistical linear mixed models with concerted efforts to control a false positive rate inflation from multiple testing. For the latter we will utilize some modality-specific methods (e.g., conditional cluster-level inference for imaging), in addition to false discovery rate control.

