Fifty participants will be recruited for this study, 25 in each group. Outcome measures, including imaging and EEG will be obtained to assess the efficacy of tDCS for a larger clinical trial. This number is based on a relatively large effect size taken from a meta-analysis of tDCS studies summarized in Price et al. (2015) Brain Stimulation, wherein some Hedge's g values were in the 0.9-1.0 range for some verbal memory and fluency measures. Given those values, we obtain a power level of 0.8 for single degree-of-freedom interaction tests. For those outcomes having lower power, we will obtain accurate effect sizes for a larger trial."

References

Alsop D.C. and Detre J.A. (1996). Reduced Transit-Time Sensitivity in Noninvasive Magnetic Resonance Imaging of Human Cerebral Blood Flow. *Journal of Cerebral Blood Flow & Metabolism*, 16, 1236–1249. doi:10.1097/00004647-199611000-00019

Altmann, A., Tian, L., Henderson, V.W., Grecius, M.D., Sex Modifies the APOE-Related Risk of Developing Alzheimer's Disease. *Ann Neurol*, 75 (4): 463-73. Doi:10.1002/ana.24135

Benninger, D. H., Lomarev, M., Lopez, G., Wassermann, E. M., Li, X., Considine, E., & Hallett, M. (2010). Transcranial direct current stimulation for the treatment of Parkinson's disease. *J Neurol Neurosurg Psychiatry*, 81(10), 1105-1111. doi: 10.1136/jnnp.2009.202556

Berlim, M. T., Van den Eynde, F., & Daskalakis, Z. J. (2013). Clinical utility of transcranial direct current stimulation (tDCS) for treating major depression: a systematic review and meta-analysis of randomized, double-blind and sham-controlled trials. *J Psychiatr Res*, 47(1), 1-7. doi: 10.1016/j.jpsychires.2012.09.025

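### The protocol names tDCS side effects but does not plan to record them or summarise them by arm, so the sham comparison gives no systematic account of tolerability

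*Combined protocol and SAP*

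**What the plan says.** **Named effects (POTENTIAL RISKS).** Four tDCS effects are described. Redness under the electrode is the most common, and of it the protocol says "This disappears within 1 hour". Itching is given the same time frame. Dizziness at the start lasts seconds. Skin damage or a burn is called very rare, small and harmless: "This gives a darkening or peeling of the top layers of skin, which normalizes after a week and heals". No rate is given for any of them.

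**Observation and response (SUBJECT SAFETY AND DATA MONITORING).** The scheduled observation is "Participants will be monitored by a clinician during administration of tDCS". With itching or burning, participants are encouraged to "inform researchers of any irritation". For burns: "If there is a burn which occurs that is evident to participant or researchers and warrants treatment, the participant will be referred" for care. RISK/BENEFIT ASSESSMENT adds: "A referral plan is in place for those who have topical skin damage from tDCS".

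**Analysis (BIOSTATISTICS).** The hypotheses for all outcome measures are group-by-time interactions from pre- to post-assessment: "We expect that tDCS-SMART will have larger post-training improvements for behavioral outcomes, EEG components, and imaging biomarker changes relative to tDCS-SHAM". The stated purpose is efficacy: "Outcome measures, including imaging and EEG will be obtained to assess the efficacy of tDCS for a larger clinical trial". No side-effect outcome or safety summary appears.

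**The concern.** The trial randomises participants between 20 minutes of stimulation and a sham switched off after 30 seconds, up to 25 per arm. That design can separate complaints caused by stimulation from those that come with electrodes, sitting still and expectation, but only if complaints are collected in the same way in both arms. As written, efficacy would be reported by arm, with no matching account of the effects the protocol itself lists.

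The planners of the larger trial would then have no tolerability data by arm from this study. A report of no burns could not be told apart from burns that were not counted. Analysts could not repair this afterwards, because the data would not have been collected systematically.

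**Working it through.** The plan states no harm rate, harm sample size or harm analysis, so there is no figure to reproduce. The check sets the sections side by side, then asks what a record could show.

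**1. Duration against scheduled observation.** Stimulation lasts 20 minutes (STUDY PROCEDURES, tDCS).

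| Effect | Stated duration | Can outlast the session? |
|---|---|---|
| Redness | up to 1 hour | yes |
| Itching | up to 1 hour | yes |
| Dizziness | a few seconds | no |
| Skin damage or burn | about a week | yes |

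Three of the four can outlast the session. No check for them is written into the next session, the post-training assessment or the three-month assessment, although all of these contacts exist.

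**2. What happens to an observed or reported effect.** The steps in SUBJECT SAFETY AND DATA MONITORING are reassurance, continuation, adjustment, discontinuation and referral. All are care steps, and none is a recording step. Referral depends on a burn warranting treatment, while POTENTIAL RISKS describes the expected damage as a few millimetres across and self-healing. A mild event could therefore occur without leading to any referral. The rule on severe adverse effects sits in the MR text, gives MR-type examples, and prescribes removal and follow-up.

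**3. Whether the analysis could absorb it.** BIOSTATISTICS frames all outcome measures as group-by-time interactions from pre to post. Side effects of a session have no pre-training value, so they do not fit that frame, and no other analysis is described.

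**4. What a record could show.** Inputs are 25 per arm and 8 sessions, from the documents. All event rates are assumed.

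- Sessions per arm: 25 × 8 = 200.
- Upper limit after 0 events in 25: two-sided 95%, 1 − 0.025^(1/25) = 0.137; one-sided 95%, 1 − 0.05^(1/25) = 0.113.
- Chance of at least one case in 25, 1 − (1 − p)^25: 0.22 at p = 1%, 0.40 at 2%, 0.72 at 5%. These values show how sparse rare events would be. They are the same whether or not anything is recorded, so they do not measure the defect.
- Power of a two-sided Fisher exact test at 0.05: 0.83 for 50% versus 10%, and 0.20 for 20% versus 5%.

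A large difference in a common effect would therefore be visible if recorded. Rare burns could only be described, with counts and an interval.

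**The case against.** A reader might infer that harms are watched for only while the current is on and that later skin harm would go unreported. The documents do not support this. The request to report irritation and the burn referral carry no stated time limit, and a referral plan is confirmed in RISK/BENEFIT ASSESSMENT. Stimulation comes immediately before a one-hour training session led by clinicians, so participants are with staff for about the hour in which redness and itching clear. They return twice a week, when a burn that takes a week to normalise could still be visible.

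A reader might also infer that observation ends about a week too early for skin damage. The stated times say when effects resolve. They do not describe delayed onset, so they do not measure missed harm.

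Nor does the list in SOURCES OF RESEARCH MATERIAL prove that harms go unrecorded. It says what materials can include, it names physical assessment data and health records, and it omits EEG and genetic data that are clearly collected.

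These objections narrow the point but leave its core. Contact with staff is not an instruction to look or to write anything down. Spontaneous report is a weak method, particularly in people enrolled for memory or cognitive complaints. No section sends tDCS effects into a data set or a table. It is also fair to say that 25 per arm tells little about rare events and that the pilot's stated aim is efficacy. That argues for description without testing, not for having no record.

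**Conclusion.** The point holds in this form: scheduled observation is limited to administration, milder or later effects would surface only by spontaneous report or chance, the documents do not say that effects are recorded, and no summary by arm is planned. The study as written would give no systematic active-versus-sham description of tolerability from up to 25 participants and 200 sessions per arm.

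This rests on the protocol's silence. A case report form outside these documents might already capture the effects, in which case only the analysis text is missing. The size of the loss cannot be stated in events, because no rates are given. The efficacy analysis is unaffected. This is a cheap improvement, not a flaw that undermines the trial.

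**What to change.** 1. **SUBJECT SAFETY AND DATA MONITORING.** Have the clinician who already attends tDCS complete the same short checklist in both arms at the end of each session: dizziness, itching or burning sensation, redness, skin damage, session discontinued, referral made. Redness is a new item, since this section does not currently mention it. Record any skin change since the last session at the start of sessions 2 to 8 and at the scheduled post-training assessment. Keep the log from outcome assessors and other blinded investigators until the blind is broken.

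2. **BIOSTATISTICS.** Report, by randomised arm, the number and percentage of participants and of sessions with each item. Give exact 95% intervals for participant-level proportions only, because sessions within a participant are not independent. No hypothesis test is needed. State that 0/25 is compatible with a true risk of up to 13.7% (two-sided 95%).

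This changes recording and reporting only. No change to stimulation, discontinuation or referral rules is proposed.

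**Cost:** a one-page checklist, one table, a short amendment and a few minutes per session, with existing staff and visits. The main care needed is for the blind, because a running log of side effects could hint at allocation.

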CONCISE SUMMARY OF PROJECT: Up to 50 individuals with memory or cognitive complaints between the ages of 50 and 80 years will be recruited for this study and may be randomized into 1 of 2 groups. These groups are reasoning training following transcranial direct current stimulation (tDCS) and reasoning training following sham transcranial direct current stimulation. The primary hypothesis is that individuals receiving tDCS prior to brain training will have a stronger response to brain training than those in the sham tDCS group.

Response to training will be measured by improved cognitive function and neural change as measured by standardized and experimental measures of cognition, MRI and EEG. A group level comparison will be done to compare the groups. Each group may consist of up to 25 participants. Participants will be comprehensively screened to rule out individuals who may have cognitive complaints which may be due to other issues such as depression, brain injury or possible dementia. Participants will be recruited from Center for BrainHealth database, as well as through flyers handed out to members of the community who attend lectures related to brain health and express an interest in future and ongoing research studies, and by means of advertisements placed in local newspapers, radio, television and magazines, and the Center for BrainHealth website. Additionally, some participants may be referred by [name] at the Alzheimer's Disease Center (ADC) of University of Texas Southwestern Medical Center. [name] is study personnel who will be reviewing participant criteria for amnestic MCI in conjunction with the clinicians, and also oversees the ADC.

STUDY PROCEDURES: The experiments described below will be undertaken with the understanding and written consent of each subject. Participants will only include people who are fluent speakers of English, as not all of the standardized and experimental cognitive tests have been normed for non-English speakers. Participants may be asked to participate in the cognitive screening and/or reasoning training portions of the study. Investigators will be blinded to which group the participants are randomized. The procedures for the study are explained below:

- **Phone Screening (20 minutes)**

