A clinician from the Center for BrainHealth will consent the participant and answer any questions before beginning the screen. The screening will consist of a medical questionnaire and MMQ which participants are given to bring into the appointment, the Mini Mental State Examination (MMSE), Geriatric Depression Scale, Auditory Selective Learning, Wide Range Achievement Test (WRAT), Logical Memory (LM) subtest, and the California Verbal Learning Test (CVLT). Participants will also undergo hearing and vision screening. Further testing for neuropsychological assessment will include standard neuropsychological measures such as the Boston Naming Test (BNT), Controlled Oral Word Association Test, Digit Span Forward and Backward (DSFB), Delis-Kaplan Executive Function System, Trails A & B, Similarities, and the Wechsler Test of Adult Reading (WTAR). Testing will also include experimental measures such as the Test of Strategic Learning, and Verbal Problem Solving, a cognitive and physical activity questionnaire, the Cognitive Reserve Index questionnaire (CRIq), and demographic scale numbers as assessed by the NAM-POWERS-BOYD Occupational Scale. Neuropsychological testing will take place on three separate occasions, so that assessment is conducted pre and post reasoning training, and three months post training. The testing will be done at the Center for BrainHealth at [name]. When a person has been seen at the ADC within the past six months, the Cognitive Screen and Neuropsychological Assessment will be shortened. Standardized neuropsychological tests will be accessed from the ADC with their permission, in order to shorten the assessment time. While participants are not being referred from Baylor AT&T Memory Center, if they have undergone testing during the past six months and would like to offer consent to have these neuropsychological batteries accessed, they will be able to do so at the consent process. At the initial neuropsychological assessment, participants will initial a portion of the consent form that indicates their willingness to undergo genotyping, with genetic information collected via a buccal swab. This is a simple procedure in which a participant's saliva is collected on a swab similar to a cotton tip swab, and sealed in a container identified with them individually and preserved for analysis. No blood sample is required. Samples will be sent to Inova Fairfax Hospital for genotyping purposes. Some participants who have already participated in the testing will be called back if they indicate willingness to the additional procedure. At the reconsent, these participants will indicate that they will only be offering a saliva sample at the time of the consent by initialing a statement on the new form, in addition to a new HIPAA form. Both consent forms will be kept for these participants, based on study procedures that were agreed to at the time of their initial consent.

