
All participants who agree to participate in reasoning training will undergo EEG, and Magnetic Resonance evaluation before and after training.

- EEG (Approx. 90 Minutes)

Each participant may undergo up to three EEG sessions, before beginning the study, at completion of the study, and three months after completing the study. Each EEG testing session may last from 60 to 90 minutes, depending upon the pace of the participant response times. All skin preparation equipment coming into contact with one's skin is thrown away after a single use, and electrodes and caps are cleaned and disinfected immediately after

use in accordance with published guidelines. EEG experiments will be conducted at the Center for BrainHealth.

- Phase 1 (Approx. 30 minutes). The electrode cap will be placed on the participant's head. Though the cap itself causes no more physical discomfort than a lycra swimcap, the application process takes time because all electrodes (up to 128) must be able to read the electrophysiological responses from the participant's scalp with a specific level of accuracy (5 kOhms). To achieve this level electrolyte gel will be added to the participant's cap. Once this level is achieved for 95% of the electrodes the experiment will begin.
- Phase 2. (Approx. 30 minutes). The participant will be asked to sit as still as possible and attend to the words/pictures that follow. For each task, the participant will be given instructions specific to that task. Because of the noise potentially recorded with neurological data, participants will see many repetitions of the same stimuli. Participants will be instructed to push the yes/no button or button 1/button 2 on the response box to indicate their response. The stimuli will be presented in blocks of 5-10 min. 2-3 minute breaks will be given between blocks for participants to rest if desired.
- Phase 3. (Approx. 5 minutes). Once the experiment has ended, the cap will be carefully removed. Participants will be offered a towel to dry their hair, and given the opportunity to wash their hair if desired.
- Debriefing. (Approx. 2-5 minutes). Participants are told about the study, and given documents pertaining to the reasoning training, and other appointments. They will be given an opportunity to ask the investigator questions about the study and their participation. They will then be thanked and debriefed.

- Magnetic Resonance Evaluation (Approx. 75 Minutes)

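### The planned group-by-time test, read as a change-score comparison, leaves baseline information unused; name a baseline-adjusted contrast for each scalar outcome

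*Combined protocol and SAP*

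**What the plan says.** The Biostatistics section frames the primary comparison for every outcome in the same way: "Our primary hypotheses for all outcome measures, including imaging and EEG, involve interactions of experimental group with pre- and post-assessment time periods". The method follows: "These will be assessed by simple interaction tests in general statistical linear mixed models". It mentions no baseline covariate and no constraint on the baseline means, and neither does any other section.

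The arms are formed by randomisation. The Concise Summary of Project says up to 50 people "will be recruited for this study and may be randomized into 1 of 2 groups", and Biostatistics sets 25 per group.

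The pre-training scores are already planned. For cognition: "Neuropsychological testing will take place on three separate occasions, so that assessment is conducted pre and post reasoning training, and three months post training". For EEG and imaging: "All participants who agree to participate in reasoning training will undergo EEG, and Magnetic Resonance evaluation before and after training".

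Biostatistics also makes estimation an aim where power falls short: "For those outcomes having lower power, we will obtain accurate effect sizes for a larger trial".

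**The concern.** With two time points, complete data and a free mean per arm and visit, the interaction term equals the difference between arms in mean change. Subtracting the whole baseline score is the most precise way to use it only when the regression slope of post on pre is 1. With equal SDs that slope is ρ, which is below 1, so the change score over-corrects and carries extra baseline noise into the estimate. Because the arms are randomised, that noise can be removed without bias, either by adjusting for the pre score or by fitting one baseline mean for both arms.

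What is at stake is precision, not validity. With 25 per arm, and with estimates meant to inform a larger trial, avoidable variance matters. The two methods can also give different estimates from the same data, so leaving the choice open allows it to be made after the results are seen. The point applies to scalar outcomes only, not to the cluster-level imaging inference.

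**Working it through.** **Inputs.** From Biostatistics: 25 per arm; Hedges' g of 0.9 to 1.0; a single degree-of-freedom interaction test; stated power 0.8. Not given, so assumed: two-sided 5%, no dropout, ρ from 0.3 to 0.9, and k = post SD / pre SD of 1, 1.25 or 0.8. The documents do not say whether g is in raw-score or change-score SDs.

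**The plan's own figure.** If g is in change-score SDs, the noncentral t with 48 df gives power 0.877 at g = 0.9 and 0.934 at g = 1.0, not 0.8. Power of 0.80 corresponds to about 0.81 change-score SDs. If g is in raw-score SDs, it corresponds to ρ of about 0.38 (g = 0.9) or 0.24 (g = 1.0). With alpha, ρ and the scale unstated, the figure cannot be reproduced. It is not shown to be wrong, and the present point does not depend on it.

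**Variance.** In units of the pre-training variance, up to the common factor 2/n:

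- Change score: 1 + k² − 2ρk, which is 2(1 − ρ) when k = 1.
- Baseline-adjusted: k²(1 − ρ²), which is 1 − ρ² when k = 1.
- Difference: (1 − kρ)², which is never negative. For k = 1 the ratio is (1 + ρ)/2 and the cut is (1 − ρ)/2.
- Cost of estimating the slope at N = 50: multiply the adjusted variance by 1 + 1/(50 − 4) = 1.022.

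Example at ρ = 0.5, k = 1: change 1.00, adjusted 0.75, ratio 0.75; with the cost, 0.75 × 1.022 = 0.766, a net cut of 23%.

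**Equal SDs (k = 1).** Power is for g = 0.9 in raw-score SDs, with 48 df (change) and 47 df (adjusted).

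| ρ | Cut before cost | Net cut | Power, change → adjusted | Detectable difference at 80% power (SD) |
|---|---|---|---|---|
| 0.3 | 35% | 34% | 0.750 → 0.898 | 0.96 → 0.78 |
| 0.5 | 25% | 23% | 0.877 → 0.945 | 0.81 → 0.71 |
| 0.7 | 15% | 13% | 0.981 → 0.991 | 0.63 → 0.58 |
| 0.8 | 10% | 8% | 0.999 → 0.999 | 0.51 → 0.49 |
| 0.9 | 5% | 3% | 1.000 → 1.000 | 0.36 → 0.36 |

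At g = 1.0, power goes from 0.833 to 0.949, 0.934 to 0.977 and 0.994 to 0.998 at ρ = 0.3, 0.5 and 0.7. If instead the change-score test really has the stated 0.80, adjustment raises it to about 0.93, 0.89, 0.85, 0.83 and 0.81 across the five values of ρ.

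Before the small-sample cost, 25 adjusted participants per arm at ρ = 0.5 are worth 25 × 1.00/0.75 = 33 per arm by change score.

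**Unequal SDs, net cut.**

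| k | ρ = 0.5 | 0.7 | 0.8 | 0.9 |
|---|---|---|---|---|
| 1.25 | 9% | 0% | −2% | 3% |
| 0.8 | 42% | 36% | 35% | 38% |

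**Simulation check** (40,000 trials per setting, 25 per arm, k = 1, true difference 0.9). Power was 0.751 against 0.899, 0.876 against 0.944, and 0.982 against 0.992 at ρ = 0.3, 0.5 and 0.7. Both estimators averaged 0.90. Under the null, rejection was 0.048–0.050 (change) and 0.047–0.051 (adjusted).

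**The same gain, seen in one trial.** The baseline difference between arms has SD √(2/25) = 0.283, so it exceeds 0.3 SD in 29% of trials for any one outcome. With equal SDs, a 0.3 SD difference shifts the change-score estimate by 0.3(1 − ρ): 0.21, 0.15, 0.09, 0.06 and 0.03 SD at the five values of ρ. The adjusted estimate is, on average, not shifted. This is not an additional benefit: 2(1 − ρ) − (1 − ρ²) = (1 − ρ)², which is exactly this shift turned into variance.

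**The case against.** The strongest reply is that the defect is inferred. The section does not say that the baseline means are free, and a mixed model with a common baseline mean would already have this precision. That stands, and it is why the point is an unspecified choice and not a wrong method. The free-mean reading is still the natural one for the wording used.

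Second, the gain is unknown and may be nil. This also stands: at k = 1 and ρ = 0.9 the net gain is 3%, and at k = 1.25 and ρ = 0.8 there is a 2% loss. That loss is the floor. At k = 1.25 and ρ = 0.8, kρ = 1, so the variance difference (1 − kρ)² is zero and only the slope cost remains.

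Third, the power figures use raw-score SDs and an unadjusted 5%, whereas the plan intends false discovery rate control. They are illustrations, not the power of the planned tests. The variance ratios depend on neither assumption.

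Fourth, training in groups of 3–5 may add group-level variance after training, and dropout may occur. Either would change the size of the gain, not its direction before the slope cost.

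Finally, some participants' baselines may be older: "Standardized neuropsychological tests will be accessed from the ADC with their permission, in order to shorten the assessment time". This applies to people seen at that centre within the past six months. Their ρ may be lower, but such scores still serve as covariates.

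**Conclusion.** The point holds as one of precision. Read as a change-score comparison, the planned test is valid and unbiased but leaves baseline information unused. With equal SDs, adjustment cuts the variance by (1 − ρ)/2 in large samples. At N = 50 the net cut is 13–34% for ρ from 0.3 to 0.7 and 3–8% for ρ of 0.8 to 0.9. With unequal SDs it ranges from a loss of about 2% to a gain of 42% in the cases worked.

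These figures assume independent participants and complete data, with ρ and the SDs chosen by assumption because the documents give none. The algebra is certain; the gain in this trial is not. The change is recommended: a small, bounded cost buys a likely gain and settles the estimator before the data are seen.

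**What to change.** In Biostatistics, replace the interaction-test sentence, for scalar outcomes, with one named contrast. Either of these would do:

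- ANCOVA of the post-training score on group and pre-training score; or
- a constrained longitudinal mixed model with one baseline mean for both arms and group-by-visit terms only after baseline, with the group difference at the post-training visit as the contrast.

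The two agree closely with complete data. The second stays within the planned model family and keeps participants who have only one of the two scores, whereas ANCOVA needs both. If a common-baseline model was always intended, one sentence saying so is enough. The cluster-level imaging inference can stay as written.

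The cost is one or two sentences, one degree of freedom and about 2% of variance at N = 50, already deducted from the net figures. No new data are needed.
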